5.2. Detailed description of PMS stages/visits

5.2.1. Baseline

- Eligibility criteria
- Cancer information
 - ✓ Diagnosis, stage
 - ✓ Metastatic lesion
 - ✓ Histopathology
 - ✓ Nephrectomy history
 - ✓ Previous cancer treatment
- Demography
 - ✓ Age
 - ✓ Gender
 - ✓ Pregnancy
 - ✓ Height and weight
- Medical history
 - ✓ Allergy history
 - ✓ Renal impairment
 - ✓ Hepatic impairment
 - ✓ Cardiovascular disease
 - ✓ Concomitant disease
- Concomitant medication
- Laboratory test result
- Tumor evaluation
- Prescription of Votrient

5.2.2. Treatment

- Safety Assessment
- Concomitant medication
- Laboratory test result
- Prescription of Votrient

Study identifier:115578
GlaxoSmithKline Korea

Protocol Ver.2

- Tumor evaluation

5.2.3. Last observation

- Safety Assessment
- Concomitant medication
- Laboratory test result
- Tumor evaluation
- Disease progression
- Survival

5.3. Safety Assessment

This is the primary endpoint of Votrient PMS. All subjects who receive at least one dose of the drug and at least once safety assessment will be safety population.

The collecting information includes, (Refer to Section 9)

- Adverse Event Term
- Onset Date
- Outcome of Adverse Event
- Intensity(refer to NCI CTCAE-V4)
- Assessment of Causality of AE
- Action taken for AE

5.4. Effectiveness Assessment

Effectiveness of Votrient is secondary end point of Votient PMS

- Overall response rate by RECIST 1.1 : (CR+PR)/evaluable for response
 - As a appendix 2, tumour evaluation can be done using RECIST 1.1 criteria
- Progression free survival (PFS)

6. PRODUCT(S) AND ADMINISTRATION

6.1. Investigational product

The medicine is not provided to the subjects by GSK. The patients will purchase the commercially available Votrient with the prescription in routine medical practice.

6.2. Dosage and administration

Votrient will be administered as described on the prescribing information. The treatment of patient does not be affected by this PMS.

7. CONCOMITANT MEDICINE

This PMS is non-interventional, therefore all concomitant medications according to local practice are allowed during the PMS and the information of drug-drug interaction may be referred to.

8. SUBJECT COMPLETION AND WITHDRAWAL

8.1. Subject completion

All subjects who receive at least one dose of the drug and at least once safety assessment will be safety population. Last observation is recommended to be conducted at 12 months after baseline in order to evaluate safety and effectiveness. If the subject do not return to follow-up visit, all data collected until the date of last contact of the subject will be used for the analysis.

8.2. Subject withdrawal

Subjects who are withdrawn because of SAEs/AEs must be clearly distinguished from subjects who are withdrawn for other reasons. Investigators will follow subjects who are withdrawn as result of a SAE/AE until resolution of the event. Withdrawals will not be replaced.

A subject is considered a 'withdrawal' from the PMS when no PMS procedure has occurred, no follow-up has been performed and no further information has been collected for this subject from the date of withdrawal/last contact.

9. ADVERSE EVENTS(AE) AND SERIOUS ADVERSE EVENTS (SAE)

During PMS, when there is a safety evaluation, the investigator or site staff will be responsible for detecting, documenting and reporting AEs and SAEs, as detailed in this section of the protocol Definition of an AE

9.1. Definition of a AE

Any untoward medical occurrence in a patient or clinical investigation subject, temporally associated with the use of a medicinal product, whether or not considered related to the medicinal product.

An AE can therefore be any unfavorable and unintended sign (including an abnormal laboratory finding), symptom, or disease (new or exacerbated) temporally associated with the use of a medicinal product. For marketed medicinal products, this also includes failure to produce expected benefits (i.e. lack of efficacy), abuse or misuse

Examples of an AE include:

- Exacerbation of a chronic or intermittent pre-existing condition including either an increase in frequency and/or intensity of the condition
- New conditions detected or diagnosed after investigational product administration even though it may have been present prior to the start of the PMS
- Signs, symptoms, or the clinical sequelae of a suspected interaction

CONFIDENTIAL

Votrient PMS

Study identifier: 115578

Protocol Ver.2

GlaxoSmithKline Korea

- Signs, symptoms, or the clinical sequelae of a suspected overdose of either investigational product or a concomitant medication (overdose per se will not be reported as an AE/SAE)
- "Lack of efficacy" or "failure of expected pharmacological action" per se will not be reported as an AE or SAE. However, the signs and symptoms and/or clinical sequelae resulting from lack of efficacy will be reported if they fulfil the definition of an AE or SAE.

Examples of an AE do not include a/an:

- Medical or surgical procedure (e.g., endoscopy, appendectomy); the condition that leads to the procedure is an AE
- Situations where an untoward medical occurrence did not occur (social and/or convenience admission to a hospital)
- Anticipated day-to-day fluctuations of pre-existing disease(s) or condition(s) present or detected at the start of the PMS that do not worsen
- The disease/disorder being studied or expected progression, signs, or symptoms of the disease/disorder being studied, unless more severe than expected for the subject condition

9.2. Definition of a SAE

A serious adverse event is any untoward medical occurrence that, at any dose:

- a) Results in death.
- b) is life-threatening.

NOTE: The term 'life-threatening' in the definition of 'serious' refers to an event in which the subject was at risk of death at the time of the event. It does not refer to an event, which hypothetically might have caused death, if it were more severe.

- c) requires hospitalization or prolongation of existing hospitalization.

NOTE: In general, hospitalization signifies that the subject has been detained (usually involving at least an overnight stay) at the hospital or emergency ward for observation and/or treatment that would not have been appropriate in the doctor's office or out-patient setting. Complications that occur during hospitalization are AEs. If a complication prolongs hospitalization or fulfills any other serious criteria, the event is serious. When in doubt as to whether "hospitalization" occurred or was necessary, the AE should be considered serious.

Hospitalization for elective treatment of a pre-existing condition that did not worsen from baseline is not considered an AE.

- d) results in disability/incapacity, or

NOTE: The term disability means a substantial disruption of a person's ability to conduct normal life functions. This definition is not intended to include experiences of relatively minor medical significance such as uncomplicated headache, nausea, vomiting, diarrhea, influenza, and accidental trauma (e.g. sprained ankle) which may interfere or prevent everyday life functions but do not constitute a substantial disruption.

- e) is a congenital anomaly/birth defect.

f) medical or scientific judgment should be exercised in deciding whether reporting is appropriate in other situations, such as important medical events that may not be immediately life-threatening or result in death or hospitalization but may jeopardize the subject or may require medical or surgical intervention to prevent one of the other outcomes listed in the above definition. These should also be considered serious. Examples of such events are invasive or malignant cancers, intensive treatment in an emergency room or at home for allergic bronchospasm, blood dyscrasias or convulsions that do not result in hospitalization, or development of drug dependency or drug abuse.

9.3. Clinical Laboratory Abnormalities and Other Abnormal Assessments as AEs and SAEs

Abnormal laboratory findings (e.g., clinical chemistry, haematology, and urinalysis) or other abnormal assessments (e.g. vital signs, etc.) that are judged by the investigator to be clinically significant will be recorded as AEs or SAEs if they meet the definition of an AE or SAE. (Refer to Section 9.1 and 9.2) Clinically significant abnormal laboratory findings or other abnormal assessments that are detected during the PMS or are present at baseline and significantly worsen following the start of the PMS will be reported as AEs or SAEs. Clinically significant abnormal laboratory findings or other abnormal assessments that are associated with the disease being studied, unless judged by the investigator as more severe than expected for the subject's condition, or that are present or detected at the start of the PMS and do not worsen, will not be reported as AEs or SAEs.

9.4. Recording of AEs and SAEs

When an AE/SAE occurs, it is the responsibility of the investigator to review all documentation (e.g., hospital progress notes, laboratory, and diagnostics reports) relative to the event. The investigator will then record all relevant information regarding an AE/SAE on the CRF.

It is not acceptable for the investigator to send photocopies of the subject's medical records to GSK in lieu of completion of the appropriate AE/SAE CRF pages. However, there may be instances when copies of medical records for certain cases are requested by GSK. In this instance, all subject identifiers will be blinded on the copies of the medical records prior to submission to GSK.

The investigator will attempt to establish a diagnosis of the event based on signs, symptoms, and/or other clinical information. In such cases, the diagnosis should be documented as the AE/SAE and not the individual signs/symptoms.

From the time a subject agree to his or her participating in this PMS until one month after he or she has completed Votrient treatment (including any follow-up period), AE/SAE will be reported promptly to GSK.

Any signs and symptoms present at the time the first dose is administered will be documented as baseline signs and symptoms. Any medical occurrences which present after administration of the medication and on or before the final follow up visit must be reported as Adverse Events. All AEs must be recorded irrespective of whether they are considered drug related. At each visit/assessment in the period defined above, AEs/SAEs will be evaluated by the investigator and recorded. Any AEs/SAEs already documented at a previous assessment and designated as ongoing, should be reviewed at subsequent visits as necessary. If these have resolved, this should be documented. If an AE changes in intensity then the maximum intensity should be captured in the CRF.

9.5. Evaluating AEs and SAEs

9.5.1. Assessment of Intensity

The investigator will make an assessment of intensity of each AE and SAE reported during PMS. The intensity of AEs and SAEs will be graded on a scale of 1 to 5 according to the National Cancer Institute (NCI) Common Toxicity Criteria for Adverse Events (CTCAE) version 4.0 and are available at <http://ctep.nci.gov/reporting/ctc.html>. (appendix 1)

9.5.2. Assessment of Causality

Every effort should be made by the investigator to explain each adverse event and assess its relationship, if any, to study drug treatment. The degree of certainty with which an adverse experience is attributed to drug treatment (or alternative causes, e.g. natural history of the underlying diseases, concomitant therapy, etc.) will be determined by how well the experience can be understood in terms of the following:

- Known pharmacology of the drug
- Reaction of similar nature being previously observed with this drug or class of drug
- The event having often been reported in literature for similar drugs as drug related (e.g. skin rashes, blood dyscrasia)
- The event being related by time to drug administration terminating with drug withdrawal (dechallenge) or reproduced on rechallenge.

If the investigator does not have all information regarding an SAE, he/she will not wait to receive additional information before notifying GSK of the event and completing the form. The form will be updated when additional information is received and forwarded to GSK. The investigator will always provide an assessment of causality at the time of the initial report. Initial notification via the telephone does not replace the need for the investigator to complete and sign the SAE Report Form

The investigator may change his/her opinion of causality in light of follow-up information, amending the SAE form.

The causality assessment is one of the criteria used when determining regulatory reporting requirements.

As per KFDA requirements, causality will be assessed as:

1. Certain:
 - The relationship of the administration and use of the drug is reasonable and it is not able to be explained by other medication, chemical substances or concomitant disease, it shows clinically reasonable response on withdrawal of the drug, the decisive case in the pharmacological or phenomenological aspect on re-challenge of the drugs if needed.
2. Probable/Likely:
 - The temporal sequence of the administration and use of the drug is appropriate and it does not seem that it is accompanied by other medications, chemical substances or concomitant disease, in the case that shows clinically appropriate response on withdrawal of the drug (no information for re-challenge).
3. Possible:
 - The temporal sequence of the administration and use of the drug is appropriate but it is also able to be explained by other medications, chemical substances or concomitant disease, and information related to withdrawal of the drug is insufficient or vague.

Study identifier: 115578
GlaxoSmithKline Korea

Protocol Ver.2

4. Unlikely:

- It is a transitory case which may not have causality with the administration and use of the drug, it is also able to be explained reasonably by other medications, chemical substances or latent disease.

5. Conditional/Unclassified:

- In the case that more information is needed for a proper evaluation or additional information is under review.

6. Unassessible/Unclassifiable:

- In the case that could not be judged due to insufficient or conflicting information and no way to complement or validate.

9.6. Follow-Up of AEs and SAEs

After the initial AE/SAE report, the investigator is required to proactively follow each subject and provide further information to GSK on the subject's condition.

All AEs and SAEs documented at a previous visit/contact and that are designated as ongoing, will be reviewed at subsequent visits/contacts.

All AEs and SAEs will be followed until resolution, until the condition stabilizes, until the event is otherwise explained, or until the subject is lost to follow-up. This applies to all subjects, including those withdrawn prematurely. The investigator will ensure that follow-up includes any supplemental investigations as may be indicated to elucidate the nature and/or causality of the AE or SAE. This may include additional laboratory tests or investigations, histopathological examinations, or consultation with other health care professionals.

GSK may request that the investigator perform or arrange for the conduct of supplemental measurements and/or evaluations to elucidate as fully as possible the nature and/or causality of the AE or SAE. The investigator is obligated to assist. If a subject dies during participation in the study or during a recognized follow-up period, the investigator will provide GSK with a copy of any post-mortem findings, including histopathology (may not be required for studies where death is an endpoint).

New or updated information will be recorded in the originally completed SAE data collection tool. The investigator will submit the updated SAE data to GSK within the designated reporting time frames.

9.7. Prompt Reporting of SAEs to GSK

9.7.1. Timeframe of SAE reporting

SAEs will be promptly reported to GSK as described in the following table once the investigator determined that the event meets the protocol definition of an SAE.

Type of SAE	Initial SAE Reports		Follow-up Information on a Previously Reported SAE	
	Time Frame	Documents	Time Frame	Documents
All SAEs	24 hrs	"SAE" CRF pages	24 hrs	Updated "SAE" CRF pages

9.7.2. Completion and Transmission of the SAE Reports

Once an investigator becomes aware that an SAE has occurred in a study subject, she/he will report the information to GSK within 24 hours or as outlined in the protocol in the section titled, "Prompt Reporting of Serious Adverse Events and Other Events to GSK". The SAE form will always be completed as thoroughly as possible with all available details of the event, and submitted to GSK within the designated time frames. If the investigator does not have all information regarding an SAE, he/she will not wait to receive additional information before notifying GSK of the event and completing the appropriate form. The SAE form will be updated when additional information is received.

The investigator will always provide an assessment of causality at the time of the initial report as described in the section of this document titled, "9.5.2 Assessment of Causality".

The primary mechanism for reporting SAEs to GSK will be the electronic data collection tool, the InForm system. If the electronic system is unavailable for greater than 24 hours, the site will use the SAE form and fax it to GSK. GSK will provide a separate list of contact details for reporting SAEs, including fax numbers and telephone numbers

9.8. Regulatory Reporting Requirements For SAEs

Prompt notification of SAEs by the investigator to GSK is essential so that legal obligations and ethical responsibilities towards the safety of subjects are met.

GSK has a legal responsibility to notify both the local regulatory authority and other regulatory agencies about the safety of a product under clinical investigation. GSK will comply with country specific regulatory requirements relating to safety reporting to the regulatory authority.

9.9. AE/SAE after end of surveillance

AE/SAE is defined as any event that occurs outside of the AE/SAE detection period as defined in the protocol. (Refer to Section 9.4)

Investigators are not obligated to actively seek AEs or SAEs in former subjects. However, if the investigator learns of any SAE, including a death, at any time after a subject has been discharged from the surveillance, and considers the event reasonably related to the drug, the investigator will promptly notify GSK.

10. REPORTING OF PREGNANCY

Any subject in person or his or her partner who becomes pregnant should be advised to discontinue Votrient. The investigator will collect pregnancy information on any subject in person or his or her partner who becomes pregnant while participating in this PMS. The investigators will record pregnancy information on the Pregnancy Report Form and submit it to GSK within 24 hours of learning of a subject's pregnancy. The subject will be instructed to inform pregnancy if investigator get this information this will be forwarded to GSK. While pregnancy itself is not considered an AE or SAE, any pregnancy complication or elective termination of a pregnancy for medical reasons will be recorded as an AE or a SAE.

Follow the subject to determine the outcome of the pregnancy and forward the outcome information to GSK no later than 6 to 8 weeks following the estimated delivery date.

11. DATA ANALYSIS AND STATISTICAL CONSIDERATION

11.1. Primary endpoint

- Occurrence of adverse events after Votrient administration by indication

11.2. Secondary endpoints

- Occurrence of unexpected or serious adverse event after Votrient administration by indication
- Effectiveness of Votrient by indication
 - Overall response rate by RECIST 1.1 : (CR+PR)/evaluable for response
 - As a appendix 2, tumour evaluation can be done using RECIST 1.1 criteria
 - Progression free survival (PFS)

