3. PMS DESIGN OVERVIEW

- Non-interventional, open-label, single group, multicenteric post-marketing surveillance in Korea.
- Indication:

Study identifier: 115578
GlaxoSmithKline Korea

Protocol Ver.2

1. Advanced renal cell carcinoma
 2. Advanced soft tissue sarcoma who have received prior chemotherapy : Adipocytic soft tissue sarcoma or gastrointestinal stromal tumors has not been demonstrated.
- Subjects treated and/or will be treated with Votrient according to the prescribing information will be enrolled.
 - Control: None
 - Data collection: Standardized electronic Case Report Form (e-CRF)

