5. ASSESSMENT OF PMS

5.1. Outline of PMS procedures

Table 1 Overview of PMS procedures

Visit	BASELINE	DURING TREATMENT ¹	LAST OBSERVATION ²
Check eligibility criteria	X		
Cancer information	X		
Demography	X		
Medical history	X		
Concomitant medication	X	X	X
Prescription	X	X	
Adverse events occurrence		X	X
Laboratory Test Results(optional)	X	X	X
Tumor assessments(optional)	X	X	X
Survival			X

1. The every-4week assessment of AE and tumor will be recommended. Disease assessment will be done by the study site's institutional standard.

2. Last observation is recommended to be conducted at 12 months after baseline excluding progression, death, drop-out (e.g. due to unacceptable AE/SAEs) or follow-up loss.

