11.4. Estimated sample size

The number of subjects to be included in this PMS was determined to be 3000 subjects as per Korean regulatory authority requirements.

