11.6.3. Analysis of effectiveness

The percentage of subjects after administration of Votrient will be tabulated.

The percentage of subjects after administration of Votrient by age, gender, past medical history, concomitant medication, the elderly, allergy, diagnosis and indication will be calculated.

- These endpoints below by indication will be calculated **Overall Response Rate**

This is defined as the percentage of subjects achieving either a complete (CR) or partial (PR) tumor response. The response rate will be calculated from the evaluation by treating physicians of best response which records of PR and CR only. Subjects with unknown or missing response will be treated as not evaluable; i.e. they will be included in the denominator when calculating the percentage. Response rates will be compared between treatment arms using stratified Fisher's exact tests. Approximate 95% confidence limits for the difference in response rates will be calculated. Exact 95% confidence limits for the tumor response rates in each arm will also be calculated

- **Progression-free survival**

This is defined as the time from initiation of medication until the earliest date of disease progression or death due to any cause, if sooner. Date of disease progression will be based on data that is captured on the case report form. At the time of analysis, for subjects who have not progressed or died, progression-free survival will be censored at the date of discontinuation of medication.

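### The response rate is labelled as RECIST 1.1, but the protocol leaves RECIST optional, so the reported rate may mix criteria under that label

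*Protocol*

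**What the plan says.** Sections 5.4 and 11.2 of the protocol give the endpoint in the same words: "Overall response rate by RECIST 1.1 : (CR+PR)/evaluable for response". In both places the next line points to Appendix 2 and says that "tumour evaluation can be done using RECIST 1.1 criteria". Appendix 2 does no more than attach the RECIST 1.1 document.

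Table 1 in section 5.1 marks tumour assessment as optional at baseline, during treatment and at last observation. Its first note recommends assessment every four weeks and adds: "Disease assessment will be done by the study site's institutional standard".

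Section 11.6.3 sets the calculation: "The response rate will be calculated from the evaluation by treating physicians of best response which records of PR and CR only". The response paragraph there does not mention RECIST, does not limit the rate to subjects assessed by RECIST, and does not split it by criteria. It keeps subjects with unknown or missing response in the denominator.

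Section 3 describes the design as "Non-interventional, open-label, single group, multicenteric post-marketing surveillance in Korea".

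**The concern.** The criteria are part of the endpoint's name, so a reader will take the reported figure as a RECIST 1.1 response rate. The protocol neither requires those criteria nor, in the items it lists for collection, asks which criteria were used. A site could follow the protocol to the letter, judge response by its own standard, and have its responses counted under the RECIST 1.1 label.

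The stake is how the result is read. Effectiveness is a stated secondary objective (section 2.2), interim reports go to the regulator (section 11.3), and public disclosure is foreseen where effectiveness is evaluated (section 12.6). The label would travel with the number, and a reader could not tell which subjects were assessed by RECIST 1.1. If the criteria are not recorded during collection, no later analysis plan can separate the two groups.

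**Working it through.** The protocol states no figure on this point, so there is nothing to reproduce. The check is a comparison of texts, followed by an illustration under assumptions.

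**Texts side by side**

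1. Endpoint name (5.4, 11.2): the rate is by RECIST 1.1.
2. Status of RECIST (5.4, 11.2, next line): permitted, not required.
3. Standard for disease assessment (Table 1, note 1): the site's own.
4. Source of the analysed response (11.6.3): the treating physician's best response, with no condition on criteria.
5. Items collected (5.2.1 to 5.2.3): tumour evaluation and disease progression, with no listed item for the criteria used.

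Item 1 claims a property that items 2 to 5 do not deliver. The drafting of the safety sections gives a useful contrast: section 9.5.1 says that intensity will be graded by CTCAE version 4.0, and section 5.3 lists that scale among the items collected. Response has neither the firm verb nor the matching item.

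The conclusion does not hang on item 3. If note 1 is read as covering timing only, items 2 and 4 still leave RECIST optional.

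**Illustration of size**

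Let s be the share of subjects judged by other criteria and d the difference in response rate between those criteria and RECIST 1.1. The pooled rate then shifts by s × d. Neither s nor d is in the protocol, and the sign of d is not known.

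- s = 20%, d = 5 points: 0.20 × 5 = 1.0 point
- s = 25%, d = 5 points: 0.25 × 5 = 1.25 points
- s = 50%, d = 10 points: 0.50 × 10 = 5.0 points
- s = 75%, d = 10 points: 0.75 × 10 = 7.5 points

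For scale, the 95% half-width is 1.96 × √(p(1 − p)/n). Take p = 0.30, the response rate that section 1.1 quotes from the renal cell carcinoma trial:

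- n = 3000 (the planned total, both indications together): 1.96 × √(0.21/3000) = 1.64 points
- n = 1500 (assumed): 1.96 × √(0.21/1500) = 2.32 points
- n = 500 (assumed): 1.96 × √(0.21/500) = 4.02 points

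The shift can fall below or above the sampling error depending on the values chosen. The protocol gives no split of the 3000 by indication and no response rate for soft tissue sarcoma. Section 11.5 limits the effectiveness population to subjects who complete all procedures, so the analysed number could be well below the enrolled number.

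**The case against.** The strongest defence is that RECIST 1.1 is the only response standard the protocol names, so the endpoint line fixes it and the line below is a loosely worded pointer to the appendix. On that view, note 1 to Table 1 concerns visit frequency, the word optional says whether a scan is done and not how it is judged, and section 11.6.3 names the assessor, who may well use RECIST. This reading is possible, and for that reason the protocol supports only that criteria *may* be mixed. If every site used RECIST 1.1, nothing would be mixed. But the permissive wording appears in both endpoint sections and no other text makes RECIST a condition, so the property remains unsecured.

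A second defence is that the eCRF and the statistical analysis plan are not shown. That stands in part: the eCRF may already hold a field for the criteria, in which case only the label and the reporting rule need attention. The endpoint's name, however, is set in the protocol itself.

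A third defence is that assessment by local practice suits a non-interventional surveillance. This is right. The defect is in the label, not in how sites assess tumours.

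A reader might also infer that progression-free survival is mislabelled. The protocol does not support that: it never calls PFS a RECIST measure, and section 11.6.3 defines it by progression captured on the case report form or death from any cause.

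**Conclusion.** The point holds as a mismatch between the endpoint's label and what the protocol secures. The rate reported as RECIST 1.1 may include responses judged by other criteria, and from what the protocol lists for collection nobody could say how many. This conclusion rests on the wording alone.

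The size is not known. A reader might infer from the illustration that the mislabelling exceeds the sampling error. That would be a product of the chosen inputs: an assumed shift of 1.0 to 7.5 points stands against half-widths of 1.64 to 4.02 points, and the values of s and d, the smaller values of n and the use of the renal cell carcinoma rate are all assumptions.

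The point is minor. The response rate is a secondary, descriptive endpoint, comparison with RECIST-based trials is not a stated objective, and the primary safety endpoint is untouched. It is still worth correcting, because the correction is cheap and the criteria may be hard to recover after collection.

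**What to change.** 1. In sections 5.4 and 11.2, rename the main endpoint 'investigator-assessed response by local standard', reported for all subjects in the effectiveness analysis whatever criteria were used.
2. Use one denominator throughout. Sections 5.4 and 11.2 divide by subjects evaluable for response, while section 11.6.3 counts not-evaluable subjects. Align the first two with 11.6.3.
3. Record in the eCRF, if it does not already do so, the criteria used: RECIST 1.1, other, clinical, or unknown. The last category is needed because section 3 admits subjects already treated, whose charts may not state the criteria.
4. Keep the label 'by RECIST 1.1' for a supplementary table, by indication, of subjects so assessed. State there that this is a selected and smaller subset with a wider interval.
5. Leave PFS as the analysis based on the case report form, and do not restrict it to RECIST-assessed subjects. Such a restriction would drop subjects who die before any tumour assessment, whose deaths count as events under section 11.6.3. Limiting the main response rate in the same way would remove subjects without an assessment and tend to inflate it.

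The cost is a change of wording in two sections, at most one eCRF field, and one table. The field adds some work for sites at each tumour assessment. No scans are added and routine care does not change.
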